### 4.1 Identification of subjects

- POTS patients will be recruited from attendees at the 2018 Dysautonomia International Patient Conference in Nashville, TN June 22-24, 2018. Announcements calling for participation will be made during the conference.
- Healthy control subjects will be recruited using Penn State Study Finder and a paper flyer.

### 4.2 Recruitment process

We will perform this study at the 2018 Dysautonomia Patient Conference in Nashville, TN. Interested participants will report to the study room. Study personal will obtain informed consent in all subjects. We will contact eligible healthy subjects through email when they respond to STUDYfinder or the paper flyer.

#### 4.3 Recruitment materials

Paper flyer

### 4.4 Eligibility/screening of subjects

The study team will go over the inclusion and exclusion criteria with subjects prior to consent.

### 5.0 Consent Process and Documentation

#### **5.1** Consent Process

# **5.1.1 Obtaining Informed Consent**

#### **5.1.1.1** Timing and Location of Consent

Interested participants will report to the study room at the conference or at Penn State Hershey Medical Center CRC. They will be asked the screening questions. If eligible, study personal will obtain informed consent in all subjects. All subjects will be given sufficient time to read the consent, all procedures will be explain in layman's terms and they will be given a copy of the signed consent form.

## 5.1.1.2 Coercion or Undue Influence during Consent

The subject will be provided with ample opportunity to have questions answered before participating in the study. All procedures will be explained to them in layman's terms and they will be given a copy of their signed consent form. Subjects will have the right to withdraw for the study at any time.

# 5.1.2 Waiver or alteration of the informed consent requirement

Not applicable

5.2	Consent Documentation			
	5.2.1	Written Documentation of Consent		
		Subjects will sign the IRB-approved consent form.		
	5.2.2	Waiver of Documentation of Consent (Implied consent, Verbal consent, etc.)  Not applicable		
5.3	Conse	nt – Other Considerations		
	5.3.1	Non-English Speaking Subjects Not applicable		
	5.3.2	Cognitively Impaired Adults		
		Not applicable		
	5.3.3	Subjects who are not yet adults (infants, children, teenagers)		
		5.3.3.1 Parental Permission  Parents will sign the IRR approved consent form		
		Parents will sign the IRB-approved consent form.  5.3.3.2 Assent of subjects who are not yet adults		
		All subjects age 13-17 will sign the IRB-approved assent form.		
HIPAA Research Authorization and/or Waiver or Alteration of Authorization				
6.1	Autho	rization and/or Waiver or Alteration of Authorization for the Uses and Disclosures of PHI		
	Check	all that apply:		
		Not applicable, no identifiable protected health information (PHI) is accessed, used or disclosed in this study. [Mark all parts of sections 6.2 and 6.3 as not applicable]		
	$\boxtimes$	Authorization will be obtained and documented as part of the consent process. [If this is the only box checked, mark sections 6.2 and 6.3 as not applicable]		
		Partial waiver is requested for recruitment purposes only (Check this box if patients' medical records will be accessed to determine eligibility before consent/authorization has been obtained). [Complete all parts of sections 6.2 and 6.3]		
		Full waiver is requested for entire research study (e.g., medical record review studies). [Complete all parts of sections 6.2 and 6.3]		
		Alteration is requested to waive requirement for written documentation of authorization (verbal authorization will be obtained). [Complete all parts of sections 6.2 and 6.3]		
6.2		or or Alteration of Authorization for the Uses and Disclosures of PHI oplicable		

# 7.0 Study Design and Procedures

Not Applicable

6.3

6.0

Waiver or alteration of authorization statements of agreement

### 7.1 Study Design

For Aim 1, this study will utilize a repeated measures design in which test scores and physiological parameters will be measured at 2 different postures (supine, standing). For Aim 2, questionnaire and exam data will be reported as percentages.

# 7.2 Study Procedures

## Step 1- Questionnaires (15 mins)

Subjects will answer questions about their POTS diagnosis, co-morbid conditions (including hEDS), and current medications, and family history. Participants will also complete standardized questionnaires including the Orthostatic grading scale, Compass 31, RAND-36, and Fatigue-VAS. All questions will be answered on tablets and data will be entered directly into REDCap. Participants will have the option to complete the questionnaires during the study visit on a tablet or after their study visit by providing their email address. A link to the questionnaires in REDCap will be emailed to participants to complete after the study visit.

# Step 3- Orthostatic Cognitive Testing (30 minutes)

Subjects will lie down on a bed for 5 minutes. Their blood pressure will be taken in triplicate while supine. Half the subjects will perform cognitive tests (stroop word color test and identification test) before standing up. The testing will take 6 minutes (3 minutes each) and the order of the tests will be randomized. Subjects will then stand up. Blood pressure and heart rate will be taken using a brachial artery oscillometric cuff every 2 minutes. While standing, the blood pressure cuff will inflate at minutes 1, 3, 5, 7, and 9 since it takes approximately 1 minute to get the recording. After 4 minutes standing, subjects will perform cognitive tests again while standing. Subjects will remain standing for up to 10 minutes. Subjects may choose to sit down and stand again to complete testing or choose to end testing at anytime. Subjects will then lie supine for 5 minutes to recover. Half of the subjects will perform cognitive testing following recovery.

The Stroop word color test is a paper-based test and correct answers recorded by a member of the research team. This test takes approximately 3 minutes to complete. The Stroop word color test evaluates executive function. Participants will be asked to name the color of ink a word is printed in, when the word itself is a different color name. For example, subjects will be shown card with a word like "yellow" but will need to say "green" not "yellow" to answer correctly. This is difficult since we read faster than we can recognize color. This is primarily an assessment of concentration ability, but also involves executive function. In a previous study by Arnold, et al. the stroop word color test was most impaired in POTS while seated (cite the prior study). However, cognitive dysfunction in POTS linked to posture is poorly understood. It is important to assess cognitive function supine and during active standing in a large sample of POTS patients. The Identification test evaluates attention based on reaction time to correct responses to "yes or no" questions. In this study, participants will be asked "is this card red?" and then will be shown a random playing card on the tablet and press the "yes" or "no" button as quickly as possible. This test will be performed using Cogstate software on a tablet and takes approximately 3 minutes to complete.

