# 1.0 Objectives

# 1.1 Study Objectives

The overall goal of this study is to investigate the impact of orthostatic stress on cognitive function in postural tachycardia syndrome (POTS), and to assess the prevalence of Hypermobile Ehlers-Danlos Syndrome (hEDS) and Hypermobility spectrum disorders (HSD) in patients with POTS. **This study will be performed in a large cohort (100 POTS patients) at the Dysautonomia International Conference in Nashville, TN June 22-24, 2018**. Healthy control subjects will be enrolled at Penn State Hershey Medical Center. The central hypothesis is that active standing in POTS worsens cognitive function and related to joint hypermobility. We will test this hypothesis in the following two specific aims:

Aim 1: Determine impact of orthostatic stress on cognition in POTS. Hypothesis 1: Active standing in POTS worsens cognitive function. Cognitive function will be assessed in the supine and standing postures using a short battery of cognitive tests. These tests examine aspects of cognition known to be impaired in POTS patients including executive function (Stroop word color test), attention (CogState Identification test), and working memory (CogState two-back test). Aim 1 will be performed in POTS patients and in healthy subjects.

Aim 2: Determine the prevalence hEDS and HSD in POTS. We will assess patients for hEDS and HSD using a questionnaire and physical exam based on the new guidelines. Aim 2 will only be performed in POTS patients.

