# 8.0 Subject Numbers and Statistical Plan

# 8.1 Number of Subjects

We will enroll up to 100 participants with Postural Tachycardia Syndrome and 50 healthy controls for this study. Subjects will participate in both aims.

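### Posture order is counterbalanced by halves, but random assignment, complementary halves and a split within POTS and controls are not stated, and no analysis accounts for sequence

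*Combined protocol and SAP*

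**What the plan says.** Section 7.2, Step 3 is the only text on posture order. It says "Half the subjects will perform cognitive tests (stroop word color test and identification test) before standing up", and later "Half of the subjects will perform cognitive testing following recovery". Between these, all subjects are tested while standing. The one reference to randomisation is "the order of the tests will be randomized". It comes straight after two tests of 3 minutes each, so in context it means Stroop versus Identification.

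Step 3 does not say how a subject is placed in either half, who decides, or that the second half consists of those not in the first. It also describes the standing session as a repeat, which is wrong for anyone not tested supine beforehand.

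On numbers, section 8.1 says "We will enroll up to 100 participants with Postural Tachycardia Syndrome and 50 healthy controls for this study". The POTS patients are tested at a conference on June 22-24, 2018. For controls, section 1.1 says "Healthy control subjects will be enrolled at Penn State Hershey Medical Center", and section 16.2 expects 5-10 of them per month, so 50 would take about 5 to 10 months (50/10 to 50/5).

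Section 8.3 plans a Wilcoxon signed-rank test by position and a Mann-Whitney test between groups, neither with a sequence or period term. Section 1.2 makes the cognitive scores primary endpoints.

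**The concern.** Each subject takes the same two tests twice within a short visit, so some gain from first to second session is plausible. The split into halves is the plan's only protection against that gain being read as a posture effect. It works only if the split is equal among the pairs analysed, within each group being analysed.

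The wording does not secure this. A half counted over all subjects can be met with different splits in POTS patients and controls, and the two groups are tested at different places and times. Section 8.3 would not correct the result. Unless the order is recorded, an imbalance could be neither seen nor adjusted for later.

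**Working it through.** **Inputs from the documents.** 100 POTS patients and 50 controls (8.1); half tested supine before standing and half after recovery (7.2, Step 3); Wilcoxon signed-rank and Mann-Whitney tests (8.3). Section 8.2 describes a convenience sample with no effect size, SD, alpha or power, so the plan has no figure to reproduce.

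**Assumptions not in the documents.** An additive practice gain *g* at the second session of 0.2 to 0.5 SD of the score; within-subject correlation 0.7; two-sided 5% tests; no true posture or group effect. Scores are oriented so that higher is better.

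**Step 1: the bias.** Let *d* be the true standing-minus-supine difference and *q* the share tested supine first. Supine-first subjects show *d + g* and standing-first subjects *d − g*. The average is *d + g(2q − 1)*.

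With shares *qP* in POTS and *qC* in controls, the bias in POTS minus controls is:
- standing scores: *g(qP − qC)*
- supine scores: *−g(qP − qC)*
- change scores: *2g(qP − qC)*

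**Step 2: equal split within each group.** With *qP = qC* = 0.5, all these terms are zero. Simulated false-positive rates were 1.8 to 3.9% for the POTS posture test and 4.4 to 6.2% for the group test at one posture.

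**Step 3: half overall but not within group.** Take 60 of 100 POTS and 15 of 50 controls supine first: (60 + 15)/150 = 50%. Then *qP* = 0.6 and *qC* = 0.3. At *g* = 0.3:
- POTS posture contrast: 0.3 × (1.2 − 1) = 0.06 SD
- group contrast at one posture: 0.3 × 0.3 = 0.09 SD
- group contrast of change: 2 × 0.3 × 0.3 = 0.18 SD

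Simulated false-positive rates for this split (1,500 runs per row):

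| *g* (SD) | POTS posture test | Group, one posture | Group, change |
|---|---|---|---|
| 0.2 | 7% | 6% | 13% |
| 0.3 | 8% | 8% | 22% |
| 0.5 | 15% | 11-12% | 48% |

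The mirror split (40 of 100 and 35 of 50) gives similar rates; at *g* = 0.3 they are 9% for posture and 23% for change.

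**Step 4: random, but not stratified by group.** If 75 of all 150 subjects were drawn at random to be tested supine first, the 95% range would be 44 to 56 of the 100 POTS patients and 19 to 31 of the 50 controls. The chance of a between-group gap of 10 percentage points or more would be about 23%.

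**Step 5: direction.** When *q* exceeds 0.5, practice favours standing and would mask a worsening. When *q* is below 0.5, it would mimic one.

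**The case against.** The strongest reply is that the protocol already counterbalances. By the formula above, an exact 50:50 split within a group removes additive practice whether or not it was randomised. That stands, and it is why the point is a risk. Bias needs an unequal split within a group, unequal completion by sequence, or a practice gain that differs by posture, sequence or group.

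The lack of stratification alone also does little to the posture test. With a random unstratified 75:75 split, its false-positive rate was about 4.2% and 3.4% for practice gains of 0.3 and 0.5 SD of the paired difference. That stands too, and it places the main exposure in the group comparison. Section 8.3 does not say whether groups are compared on change or at each posture; at one posture the bias is half as large.

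Four stronger readings are tempting, and the documents do not support them:
- **That posture order is not randomised.** The text is silent on this; it does not say that assignment is non-random.
- **That splits as extreme as 80:20 in POTS are in play.** Half of 150 is 75, so 80 supine-first POTS patients would break the protocol's own rule.
- **That patient condition biases the posture comparison.** A stable condition cancels in a paired difference.
- **That staff choose the order after seeing the patient.** No section describes this. It is only not excluded.

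Completion cuts the other way. Step 3 says "Subjects may choose to sit down and stand again to complete testing or choose to end testing at anytime". A standing-first subject who stops may never give a supine score, so the analysed pairs can be unequal even when the assignment was equal.

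**Conclusion.** The concern holds as a gap in the specification with a real but conditional consequence. The plan does not secure a random, complementary split of posture order within each group, and its analysis would not correct for an unequal one.

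In the worked split, which meets the half rule overall, false positives are about 13 to 48% on a group comparison of change and about 7 to 15% on the POTS posture test. These figures rest on the assumed practice gain, the correlation of 0.7 and an illustrative imbalance; the documents give no value for any of them. With equal splits within each group, additive practice produces no bias. The error can run either way, so a reader should not infer that the design favours the study hypothesis. The change is worth making because it costs almost nothing.

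**What to change.** 1. In section 7.2, Step 3, replace both sentences about halves with: *Posture order (supine-standing or standing-supine) is assigned 1:1 from a computer-generated permuted-block list, separately for POTS patients and controls, opened after eligibility and consent. Each subject has one supine and one standing test session.*
2. Reword the description of the standing session so that it also fits subjects tested standing first.
3. Record assigned and actual order in REDCap, and report completion of both sessions by order and group.
4. In section 8.3, stratify both comparisons by sequence, so that unequal completion does not bring the practice effect back:
   - **Posture, within each group:** compare second-minus-first differences between the two sequences with a Mann-Whitney test. These are *d + g* and *−d + g*. They differ by *2d*, so additive practice drops out whatever the split. Simply pooling signed-rank tests across sequences would not achieve this.
   - **POTS versus controls:** use a rank test stratified by sequence (van Elteren), and state whether the comparison is on change or at each posture. This removes practice if the gain is similar in the two groups.

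Neither analysis repairs other effects of selective stopping, which is why completion should be reported.

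**Cost:** one list per group, a few sentences in Step 3 and section 8.3, and two REDCap fields. No extra subjects, visits or testing time.

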#### 8.3 Statistical methods

We will compare cognitive testing results by position using Wilcoxon signed-rank tests. Results will be compared between groups (POTS, controls) using Mann-Whitney U test.

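### The cuff inflates during the standing tests and is not scheduled to during the supine tests, so the posture comparison also compares cuff with no cuff

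*Combined protocol and SAP*

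**What the plan says.** Section 7.2, Step 3 sets out the session. Subjects rest supine for 5 minutes, and "Their blood pressure will be taken in triplicate while supine". Half of them then take the Stroop and Identification tests, 3 minutes each in random order. All subjects stand, and "After 4 minutes standing, subjects will perform cognitive tests again while standing". Standing lasts at most 10 minutes. A 5-minute supine recovery follows, and "Half of the subjects will perform cognitive testing following recovery".

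For the standing period the protocol states that "the blood pressure cuff will inflate at minutes 1, 3, 5, 7, and 9 since it takes approximately 1 minute to get the recording". The sentence before it gives a two-minute reading interval without naming a posture, but it comes directly after the instruction to stand. The only minutes listed anywhere are for standing. No inflation is scheduled during the supine tests, whether these come before standing or after recovery.

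Cognitive scores are a primary endpoint (section 1.2). The analysis in section 8.3 is: "We will compare cognitive testing results by position using Wilcoxon signed-rank tests". The same section adds a Mann-Whitney comparison of POTS with controls but does not say whether scores or supine-to-standing changes are compared.

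**The concern.** Hypothesis 1 is that standing worsens cognition in POTS, and it is tested within subjects by comparing positions. That comparison isolates posture only if the test conditions are otherwise alike. Here a second condition, an inflating arm cuff, goes with standing in every subject.

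The protocol's own descriptions make distraction plausible. On one test, "The Identification test evaluates attention based on reaction time to correct responses"; of the Stroop it says "This is primarily an assessment of concentration ability, but also involves executive function". Section 11.0 accepts that frequent cuff readings may be uncomfortable.

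The existing safeguards do not separate the two conditions. Placing the supine tests before standing in half the subjects and after recovery in the other half can balance practice, but the cuff accompanies standing in both halves. Randomizing test order only decides which test meets more inflations. A cuff effect common to POTS and controls would cancel if changes were compared between groups, but the within-POTS test would remain exposed.

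**Working it through.** **Inputs.** From section 7.2, Step 3: tests start at standing minute 4; two tests of 3 minutes; inflations at minutes 1, 3, 5, 7 and 9; about 1 minute per recording; standing at most 10 minutes. From section 8.1: "We will enroll up to 100 participants with Postural Tachycardia Syndrome and 50 healthy controls for this study".

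**1. Test window.** 4 + 2 × 3 = 10, so the standing tests occupy minutes 4 to 10. This agrees with the stated 10-minute maximum.

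**2. Overlap when standing.** Three of the five inflations (5, 7, 9) fall in the window, at 1, 3 and 5 minutes into the test block. Recording time is 3 × 1 = 3 of 6 minutes (50%).
- If a recording took 0.5 to 1.5 minutes (assumed range), the overlap would be 1.5 to 4.5 minutes (25% to 75%).
- The first test (minutes 4–7) meets one inflation and the second (7–10) meets two.
- If testing began as late as minute 5.5, all three recordings would still overlap it.
- If the listed minutes mark the end of a recording, the recordings run 4–5, 6–7 and 8–9, again three in the window.

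**3. Overlap when supine.** Scheduled inflations during the tests: 0 of 6 minutes, in either order half.

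**4. What a cuff effect would do to the test (illustration only).** The documents give no cuff effect, so the shifts below are assumed. They are in units of the SD of the paired difference, with no true posture effect, normal differences, a two-sided 5% signed-rank test and 20,000 simulated trials per cell.

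| Cuff shift (SD) | Rejection, n = 100 | n = 80 | n = 60 |
|---|---|---|---|
| 0 | 0.050 | 0.050 | 0.048 |
| 0.02 | 0.051 | 0.053 | 0.051 |
| 0.05 | 0.073 | 0.072 | 0.063 |
| 0.1 | 0.163 | 0.144 | 0.113 |
| 0.2 | 0.490 | 0.405 | 0.318 |
| 0.3 | 0.826 | 0.735 | 0.600 |

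The normal approximation agrees. With signed-rank efficiency 3/π = 0.955, rejection ≈ Φ(δ√(0.955n) − 1.96) + Φ(−δ√(0.955n) − 1.96). For n = 100, √95.5 = 9.77:
- δ = 0.1: Φ(−0.98) + Φ(−2.94) ≈ 0.16
- δ = 0.2: Φ(−0.01) ≈ 0.50
- δ = 0.3: Φ(0.97) ≈ 0.83

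**5. Comparing changes between groups.** For a Mann-Whitney test on the supine-to-standing change, 100 against 50, a cuff shift common to both groups (0.05 to 0.3 SD) leaves rejection at 0.049 to 0.050. Its power for a true excess change in POTS of 0.2, 0.3 or 0.5 SD is 0.200, 0.390 or 0.800. Check at 0.3: 0.3 × √(0.955 × 100 × 50 / 150) = 1.69, and Φ(1.69 − 1.96) = Φ(−0.27) ≈ 0.39. The within-POTS test of a 0.3 SD change has about 83% power.

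**The case against.** The supine half of the argument rests partly on silence. The three supine readings have no stated minutes, and their place before the tests is inferred from sentence order. The two-minute interval names no posture, and because the next sentence opens by limiting itself to standing, one could argue that the interval was meant more widely. This stands as a limit. However, the interval follows the instruction to stand, and staff following the text would find no supine inflation times to apply.

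No cuff effect has been shown. Section 11.0 speaks of discomfort, not of test performance, and the rejection rates describe a signed-rank test under any shift at all. This is correct, and it is why the rates are only an illustration.

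A common cuff effect should also appear in the controls' own supine-standing comparison. This is a partial check: 50 controls would detect a shift of 0.2 SD with about 28% power and 0.3 SD with about 54%, and they cannot reveal an effect specific to POTS.

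Finally, each test meets only one or two inflations, and subjects who sit or stop early may meet fewer. That reduces the imbalance without removing it.

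**Conclusion.** The concern holds. Followed as written, the schedule makes the two postures differ in cuff inflation as well as posture: up to about 3 of 6 test minutes for a subject who stands throughout, against 0 of 6 scheduled supine. This affects the within-subject test of Hypothesis 1 on a primary endpoint.

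What is established is a removable difference in test conditions, not a demonstrated bias. Its consequence depends on a cuff effect whose size and direction the documents do not give. That consequence is negligible below about 0.05 SD of the paired difference and substantial from about 0.2 SD upward. The conclusion assumes that the supine triplicate is taken before the tests and that the two-minute interval applies to standing. Confidence is medium. The change should be made because it costs little and no existing safeguard covers the within-POTS test.

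**What to change.** Add one sentence to section 7.2, Step 3: during the supine test block the cuff inflates at 1, 3 and 5 minutes after the tests start, in both order halves and in both POTS and control subjects. This matches standing minutes 5, 7 and 9. Leave the standing readings unchanged, since blood pressure and heart rate during standing are a secondary endpoint (section 1.3). If the two-minute interval was always meant to cover supine testing, the sentence simply makes that explicit.

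The cost is three more automatic readings with equipment already in use, and no added visit time because they run during the tests. There is slight extra arm discomfort, and supine scores will then describe cognition with the cuff running. Matching does not exclude a cuff effect that itself differs by posture.

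Stating in section 8.3 that supine-to-standing changes are compared between groups is a useful addition but not a substitute. It has less power and cancels the cuff effect only if that effect is equal in POTS and controls.

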# 1.2 Primary Study Endpoints

Our primary endpoints are the scores on the cognitive tests and the Beighton score.

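### Sitting, re-standing and stopping are allowed during a standing test with no slack, yet nothing calls for recording them or separates post-rest from uninterrupted standing scores, so the posture effect may be biased, most plausibly toward none

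*Combined protocol and SAP*

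**What the plan says.** Section 1.1 sets out the claim to be tested: "Hypothesis 1: Active standing in POTS worsens cognitive function". Section 1.2 makes the test scores primary: "Our primary endpoints are the scores on the cognitive tests and the Beighton score".

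Section 7.2, Step 3 gives the timetable:
- Start of standing tests: "After 4 minutes standing, subjects will perform cognitive tests again while standing".
- Length: "The testing will take 6 minutes (3 minutes each) and the order of the tests will be randomized".
- Ceiling: "Subjects will remain standing for up to 10 minutes".
- Interruption: "Subjects may choose to sit down and stand again to complete testing or choose to end testing at anytime".
- Supine testing comes before the stand for half the subjects. For the others: "Half of the subjects will perform cognitive testing following recovery".

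Section 8.3 is the whole analysis plan. Within subjects: "We will compare cognitive testing results by position using Wilcoxon signed-rank tests". Between POTS patients and controls it names the Mann-Whitney U test. It gives no rule for a score that is missing, cut short or obtained after a seated rest, and no sensitivity analysis. Section 10.3 provides paper worksheets for physiological variables and well-being, but no section asks for test start and finish times, sit-downs or early endings. Section 3.3.2 requires no follow-up of those who withdraw.

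**The concern.** Completing the tests after sitting down is a route the protocol itself offers. A score obtained that way carries the same label as one from an unbroken stand. Ending early leaves one or both standing scores missing, and a signed-rank test can only use subjects with both members of the pair. A subject in the supine-last half who ends testing may lose the supine score too.

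These events are unlikely to be random. Section 2.2 describes POTS as chronic orthostatic intolerance, and section 3.2 excludes only those unable to stand, so people who can stand but tolerate it poorly are enrolled. Sitting or stopping is then plausibly a consequence of the exposure under study. Controls must be free of chronic illness and recurrent syncope. If they stop less often, which is an assumption, the group comparison is exposed as well.

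A null result could be read as showing that standing does not impair cognition in POTS, when the scores behind it came partly from rested patients and partly from those who tolerate standing best. If interruptions are not logged at the visit, no later analysis can reliably separate the two kinds of score.

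**Working it through.** The plan has no figure to reproduce: sections 8.2 and 8.3 give no alpha, power, effect size, SD or expected loss.

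**Timetable (section 7.2, Step 3).** Start at 4 min + two tests of 3 min each = 10 min, against a ceiling of 10 min, so slack = 0. The first test runs from about minute 4 to 7 and the second from about 7 to 10. A stop before minute 7 spoils both. A stop between 7 and 10 spoils only the second. Test order is randomized, so the loss is spread over the two tests.

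**Assumed inputs (none is in the documents, except n).** Paired change, worsening positive, normal with mean 0.30 and SD 1; n = 100 POTS patients (the section 8.1 maximum); two-sided 5% Wilcoxon test; a fraction p with the highest propensity to stop or sit; correlation r between that propensity and worsening.

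**Case A: stoppers drop out of the pairs.** Mean change among those remaining = 0.30 - r × φ(z)/(1 - p), where z is the (1 - p) normal quantile.
- p = 0.20: φ(z)/(1 - p) = 0.280/0.80 = 0.350
- p = 0.10: φ(z)/(1 - p) = 0.1755/0.90 = 0.195

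| r | 10% lost | 20% lost |
|---|---|---|
| 0.7 | 0.30 - 0.137 = 0.16 | 0.30 - 0.245 = 0.055, about 0.06 |
| 0.3 | 0.30 - 0.059 = 0.24 | 0.30 - 0.105 = 0.195 |
| 0.2 | 0.30 - 0.039 = 0.26 | 0.30 - 0.070 = 0.23 |
| 0 | 0.30 | 0.30 |
| -0.3 | 0.30 + 0.059 = 0.36 | 0.30 + 0.105 = 0.405, about 0.41 |

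Simulated power is about 82% with complete data. With 20% lost it is about 73% at r = 0, 53% at 0.2, 40% at 0.3 and 12% at 0.7.

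**Case B: subjects sit, re-stand and finish, and rest is assumed to remove half of any worsening.** At r = 0 the mean positive part of the change is 0.30 × Φ(0.30) + φ(0.30) = 0.30 × 0.618 + 0.381 = 0.567. With 20% affected, the mean effect is 0.30 - 0.20 × 0.5 × 0.567 = 0.24. By simulation it is 0.18 at r = 0.6 and 0.27 at r = -0.3, so it stayed below 0.30 at every correlation tried.

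**Case C: a truncated test is scored as it stands, with an assumed extra loss of 0.5 SD.** 0.30 + 0.20 × 0.5 = 0.40 with 20% affected, and 0.30 + 0.10 × 0.5 = 0.35 with 10%. This is bias away from none.

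A given score is either missing, post-rest or truncated, so the three cases should not be added together.

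**The case against.** Several stronger readings are tempting, and the documents do not support them.

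A reader might infer that the plan prescribes a completer analysis. It does not: section 8.3 is silent, and complete pairs are only the natural default of a signed-rank test. Section 8.3 also does not say whether the Mann-Whitney test uses changes or scores at one posture, so a missing standing score need not remove a subject from every group comparison.

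A reader might infer that the bias is certainly toward none. Case A gives no bias at r = 0 and bias the other way at -0.3, and Case C also exaggerates the effect. Section 2.2 reports cognitive symptoms even when supine and suggests that impairment is not purely postural, so a strong link between intolerance and posture-specific worsening is uncertain. The severe results at correlation 0.7 illustrate a mechanism and are not estimates for this study.

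A reader might infer that anyone who ends early has no standing score. Someone who stops after about minute 7 can have one complete test. The permission to re-stand also helps to retain patients who tolerate standing poorly, and their remaining testing is done standing.

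A worst-rank analysis might seem the obvious safeguard, with a null accepted only if it agrees. That gate is unsound. With no cognitive effect, n = 100 and stoppers given the largest worsening ranks, the signed-rank test was significant in about 11%, 35% and 95% of simulated trials with 5, 10 and 20 stoppers. A true null could seldom be reported.

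These objections narrow the point but do not remove it. A primary endpoint still mixes two kinds of score under one label, with no record called for that would separate them.

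**Conclusion.** The concern holds in this limited form. The protocol plans for interrupted standing tests on a timetable without slack, calls for no record of the interruptions, and does not distinguish post-rest from uninterrupted scores before the section 8.3 tests. The resulting bias is most plausibly toward none, because post-rest scores are likely to be attenuated and poorly tolerant patients are likely to be missing from the pairs. Neither the direction nor the size is established.

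Under the assumed 0.30 SD effect, n = 100 and 20% loss, the completer effect spans about 0.06 to 0.41 SD as the correlation runs from 0.7 to -0.3. That range rests wholly on assumed values and shows how far the result could depend on an unrecorded event. The change should be made, because it is cheap and an interruption that goes unlogged at the visit probably cannot be recovered.

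**What to change.** 1. On the existing worksheet, log for each cognitive test the start and finish minute and whether the subject sat, re-stood or ended.
2. Run the Wilcoxon test on all available paired scores, stating beforehand whether a test broken off part-way yields a score. As a pre-specified sensitivity analysis, repeat it on pairs whose standing test was started and finished without sitting. This subset is more selected, so it belongs beside the main analysis and does not replace it.
3. Report the percentage completing each test uninterrupted, by group and by supine-first or supine-last half. If completion is incomplete or differs between groups, limit the conclusion to those tested.
4. If a worst-rank analysis is shown, label it a composite of standing intolerance and cognition. It is not evidence on cognition alone and must not serve as a condition for interpreting a null.

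The cost is a few worksheet fields, one extra test per measure, a completion table and a smaller sample in the sensitivity analysis. Neither analysis recovers scores that were never obtained. The subject's freedom to sit or stop is unchanged.
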